10.4 TUMOUR RESPONSE ASSESSMENT ACCORDING TO MODIFIED RECIST 1.1 CRITERIA

The RECIST response evaluation criteria version 1.1 will be adhered to as described in the guidelines published in the European Journal of Cancer ([R09-0262](#)) and the accompanying articles. Trial personnel involved in tumour assessment for this trial must be trained and knowledgeable of RECIST criteria version 1.1.

Tumour assessments should include CT scans of the chest, abdomen, pelvis and a brain CT/MRI as well as a bone scan at screening. If clinically indicated, imaging of any other known or suspected site of disease (e.g. breast) using an appropriate method (CT scan, MRI, etc.) should be performed. The same radiographic procedure must be used throughout the trial. All images acquired and skin lesion photos will be sent to a central imaging CRO. If mammography is additionally conducted during clinical routine, it should also be sent for central imaging assessment together with any correlative images. Breast-ultrasound and biopsy data, if available, will be provided to the central imaging CRO for independent review by Sponsor data management. As of 29 Oct 2021 due to the outcome of the study, images no longer will need to be sent to CRO for independent review.

The preferred method of assessment is a spiral CT scan with i.v. and oral contrast, unless i.v. and/or oral contrast are medically contraindicated. Scans of the abdomen, pelvis and other areas of the body, but not chest, may be done with MRI instead of CT.

Skin lesions followed as target lesions must be documented by colour digital photography and must include in the image a ruler with millimetre subdivisions and a label that includes the patient's ID and exam date.

Bone scans (using 99m-technetium polyphosphonate scintigraphy) must be done at screening. During the trial, bone scans must then be repeated as specified in the [Flow Chart](#) with every other CT scan in patients with bone metastasis at baseline. An additional bone scan will be performed at week 8. A bone scan shall always be assessed in correlation with anatomical imaging, CT, MRI, using a combination of modified RECIST 1.1 with MDA criteria ([Table 10.4:4](#)), as outlined in detail below in [Tables 10.4:1](#) and [10.4:2](#) for target and non-target lesions.

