Modified RECIST version 1.1: All measurable lesions up to a maximum of five lesions in total can be selected. These five lesions shall be representative of all involved non-visceral anatomical locations. However if a patient presents with target lesions only in bone or in lymph nodes or in soft tissue, five lesions within one anatomical location, bone, nodes, soft tissue, can be identified as target lesions. The longest diameter (LD) will be measured for all lesions except lymph nodes, for which shortest diameter (SD) perpendicular to the LD is used. All target lesions will be recorded and numbered at baseline. Target lesions should be selected on the basis of their size and their suitability for accurate repetitive measurements (either by imaging techniques or clinically).

A sum of diameter (SOD) for all target lesions will be calculated (using ShD for lymph nodes and LD for all other lesions) and reported as the baseline SOD. The baseline SOD will be used as reference to further characterise the objective tumour response of the measurable dimension of the disease (see [Table 10.4: 1](#)).

Table 10.4: 1 Evaluation of target lesions with rules for bone lesions according to RECIST 1.1 and modified MDA criteria

Complete Response (CR)
 
For target bone lesions:
	
Disappearance of all target lesions. Any pathological lymph nodes must have reduction in short axis to <10 mm.
 
 • Complete sclerotic fill-in of lytic lesions on XR or CT • Normalization of bone density on XR or CT • Normalization of signal intensity on MRI • Normalization of tracer uptake on bone scan

Partial Response (PR)
 
For target bone lesions:
	
At least a 30% decrease in the SOD of all target lesions taking as reference the baseline SOD.
 
 • Development of a sclerotic rim or partial sclerotic fill-in of lytic lesions on XR or CT. • Osteoblastic flare • re - Interval visualization of lesions with sclerotic rims or new sclerotic lesions in the setting of other signs of PR and absence of progressive bony disease • subjective decrease in tracer uptake on bone scan

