
Stable Disease (SD)
 
For target bone lesions:
	
Neither sufficient shrinkage to qualify for PR, less than 30% decrease, taking as reference the baseline SOD, nor sufficient increase to qualify for PD, less than 20% increase, taking as reference nadir, the smallest SOD recorded on study (including baseline).
 
No new bone metastases.

Progression (PD)
 
For target bone lesions:
	
At least a 20% increase in the SOD of all target lesions taking as reference the smallest SOD (nadir) recorded on study (including baseline), together with an absolute increase in the SOD of at least 5 mm.
 
OR
 
The appearance of one or more new unequivocal lesions.
 
 • Subjective increase in tracer uptake on bone scan • New bone metastases

All other lesions (or sites of disease) should be identified as non-target lesions and should also be recorded at baseline. Measurements are not required and these lesions should be followed as “present” or “absent” (see [Table 10.4: 2](#)).

Table 10.4: 2 Evaluation of non-target lesions and new lesions with rules for bone lesions according to RECIST 1.1 and modified MDA criteria

Complete Response (CR)
 
For non-target bone lesions:
	
Disappearance of all non-target lesions. All lymph nodes must be non-pathological in size (<10 mm short axis)
 
 • Complete sclerotic fill-in of lytic lesions on XR or CT • Normalization of bone density on XR or CT • Normalization of signal intensity on MRI • Normalization of tracer uptake on bone scan

Non-CR/Non-PD
 
For non-target bone lesions:
	
Persistence of one or more non-target lesions
 
 • Development of a sclerotic rim or partial sclerotic fill-in of lytic lesions on XR or CT • Osteoblastic flare – • Interval visualization of lesions with sclerotic rims or new sclerotic lesions and absence of progressive bony disease • subjective increase or decrease in the size of ill-defined lesions on XR, CT, or MRI not sufficient for either PD or CR • subjective increase or decrease in tracer uptake on bone scan not sufficient for PD or CR

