
Progression (PD)
 
For non-target bone lesions:
	
Appearance of one or more new lesions and/or unequivocal progression of existing non-target lesions.
 
 • Subjective substantial increase in the size of ill-defined lesions on XR, CT, or MRI • Subjective substantial increase in tracer uptake on bone scan • New bone metastases

In some circumstances it may be difficult to distinguish residual disease from normal tissue. When the evaluation of complete response depends upon this determination, it is recommended that the residual lesion be investigated (fine needle aspirate/biopsy) before confirming the complete response status if in accordance with standard of care and after consent from patient based on institutional guidelines.

Evaluation of best response to study treatment

The best response to study treatment is the best response recorded from the start of treatment until disease progression or start of further anti-cancer treatment (taking as reference for progressive disease the smallest SOD recorded on study). The tables below are showing the time point response for patients with target ([Table 10.4: 3](#)) and non-target only disease ([Table 10.4: 4](#)). The time point responses for each patient are used to determine their best response to trial treatment.

Patients with a global deterioration of health status requiring discontinuation of treatment without objective evidence of disease progression at that time should be reported as “symptomatic deterioration”. Every effort should be made to document the objective progression even after discontinuation of treatment.

Table 10.4: 3 Time point response: patients with target disease

Target lesions	Non-target lesions	New lesions	Overall response
CR	CR	No	CR
CR	Non-CR/ Non-PD	No	PR
CR	Not evaluated	No	PR
PR	Non-PD or not evaluated	No	PR
SD	Non-PD or not evaluated	No	SD
Not evaluated	Non-PD	No	NE
PD	Any	Yes or No	PD
Any	PD	Yes or No	PD
Any	Any	Yes	PD

Table 10.4: 4 Time point response: patients with non-target disease

Non-target lesions	New lesions	Overall response
CR	No	CR
Non-CR / non-PD	No	Non-CR / non-PD ^a
Not all evaluated	No	NE
Unequivocal PD	Yes or No	PD
Any	Yes	PD

A “Non-CR/non-PD is preferred over “stable disease” for non-target disease since SD is increasingly used as an endpoint for assessment of efficacy in some trials so to assign this category when no lesions can be measured is not advised.

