Response evaluation rules for bone lesions aligned with the MDA criteria

Target and non-target assessment are adapted in alignment with the MDA criteria ([R17-4024](#); see [Table 10.4: 5](#)). Bone lesion measurements will not be performed perpendicular bidimensional, as described in MDA, but unidimensional following RECIST 1.1. The %-changes of target lesion measurements follow RECIST 1.1, at least 30% decrease for PR and at least 20% increase for PD accordingly. Non target lesions’ assessment will not be based on quantitative analysis, but according to RECIST 1.1 on qualitative assessment only.

In this patient population with predominantly osteolytic or mixed skeletal metastases from breast cancer, a mere lesion counting on bone scans is not sufficient and would be medical incorrect and unacceptable. Thus a combination of the RECIST-defined assessment of bone lesions in conjunction with the more detailed description of a joined assessment of bone scan and anatomical imaging is scientifically reasonable. 99m-technetium bone scan alone may show metabolic activity with tracer uptake, which could be misinterpreted as a false positive progression for responding and healing lesions, and vice versa non-activity with lack of tracer

uptake could be misinterpreted as false negative implying response, PR or CR, for metabolically inactive lesions. CT or MRI alone may only detect large bone lesions but may not be sensitive enough for small, faint or new lesions. The combined evaluation with both methods and both criteria thus allows for a more detailed, more precise assessment of the skeletal disease and its response to treatment or lack thereof.

Table 10.4: 5 MD Anderson (MDA) criteria*

Response category	Criteria
Complete Response	Complete sclerotic fill-in of lytic lesions on XR or CT Normalization of bone density on XR or CT Normalization of signal intensity on MRI Normalization of tracer uptake on BS
Partial Response	Development of a sclerotic rim or partial sclerotic fill-in of lytic lesions on XR or CT. Osteoblastic flare - Interval visualization of lesions with sclerotic rims or new sclerotic lesions in the setting of other signs of PR and absence of progressive bony disease $\geq 50\%$ decrease in measurable lesions on XR, CT, or MRI $\geq 50\%$ subjective decrease in the size of ill-defined lesions on XR, CT, or MRI $\geq 50\%$ subjective decrease in tracer uptake on SS

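### Protocol Appendix 10.4 sets a lower bone-scan uptake bar for progression in target bone lesions than in non-target ones, without explanation (minor)

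*Protocol*

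**What the plan says.** All the rules are in Protocol Appendix 10.4.

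- **Target bone lesions (Table 10.4: 1).** The progression row has two bone bullets. One is new bone metastases; the other is "Subjective increase in tracer uptake on bone scan". The only bone line in the stable-disease row is "No new bone metastases".
- **Non-target bone lesions (Table 10.4: 2).** The progression bullet reads "Subjective substantial increase in tracer uptake on bone scan". A smaller change has its own place under Non-CR/Non-PD: "subjective increase or decrease in tracer uptake on bone scan not sufficient for PD or CR".
- **Source criteria (Table 10.4: 5).** The published MDA rule for progression by uptake is a subjective increase of at least 25%.
- **Stated adaptations.** The text before Table 10.4: 5 names three: one-dimensional measurement, RECIST percentages for size ("The %-changes of target lesion measurements follow RECIST 1.1"), and qualitative assessment of non-target lesions. Protocol section 5.1 says more generally that the MDA criteria are clarified and modified, and the titles of Tables 10.4: 1 and 10.4: 2 call them modified MDA.
- **Safeguards.** "A bone scan shall always be assessed in correlation with anatomical imaging, CT, MRI". The appendix also warns that uptake on a bone scan alone can mislead, "which could be misinterpreted as a false positive progression for responding and healing lesions". Signs of healing are listed under partial response in Table 10.4: 1, including "Development of a sclerotic rim or partial sclerotic fill-in of lytic lesions on XR or CT" and osteoblastic flare.

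**The concern.** The same sign on the same scan meets different bars depending only on whether the lesion was chosen as a target at baseline. The target lesion, which also has a measured diameter to rely on, gets the looser uptake rule. The target table has no stated place for a rise short of progression, although the authors wrote such a place into the non-target table.

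Table 10.4: 3 turns target progression into overall progression whatever else is seen, and independently assessed progression dates PFS, the primary endpoint (Protocol section 7.3.1). If a reader took the bullet at face value, a modest rise in a stable or healing bone lesion would become a PFS event. With about 40 events planned, a few such calls would blur the hazard ratio.

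**Working it through.** No figure in the plan depends on this rule, so the main check is a comparison of texts.

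**1. Order the bars.** Uptake increase needed for progression: target, any subjective increase; non-target, a substantial one; source MDA, at least 25%. The target rule is the loosest of the three.

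**2. Run one case through the tables.** Take a target bone lesion with a sum of diameters up by less than 20%, no new metastasis, and uptake modestly higher. The stable-disease row is met, because size is within limits and there is no new bone lesion. The uptake bullet in the progression row is also met. Reclassify the lesion as non-target and the answer is Non-CR/Non-PD only. Under the source MDA rule a rise below 25% is not progression.

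**3. Is the bullet sufficient by itself?** The table does not say. The other bullet in that list, new bone metastases, is sufficient alone, so the layout does not show that the uptake bullet is only supportive.

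**4. Do the safeguards decide the case?** They require the bone scan and CT or MRI to be read together, and they warn against relying on uptake alone. They do not say which finding prevails when uptake rises modestly and CT is stable. They lower the risk without removing the overlap.

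**5. Scope.** Bone lesions under 10 mm, or not lytic or mixed, are non-measurable and so fall under Table 10.4: 2. Only patients with measurable lytic or mixed bone targets are affected. The documents do not give their share.

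**6. Illustration of size, on assumed rates.**

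- Inputs from Protocol section 7.7: 80 patients over 15 months, control median 9.9 months, true HR 0.50, analysis at 40 events, 20% lost. Assumed here: losses fall uniformly over 0 to 15 months, and progression is dated at the next scheduled CT.
- Assumptions with no source in the documents: 20% to 40% of patients have target bone lesions, and 5% to 20% of those are called progressed at week 8 without true progression, equally in both arms.
- Patients flagged: 80 × 0.20 × 0.05 = 0.8 up to 80 × 0.40 × 0.20 = 6.4. Some will already have progressed or been lost. In 20,000 simulated trials per scenario, 0.7 to 5.7 of the 40 events are affected.
- SE of log HR = 2/√40 = 0.316. This reproduces the plan's own figure: Φ(ln(0.60/0.50)/0.316) = Φ(0.577) = 71.8%, as in Table 7.7: 1.
- The median estimated HR is 0.515 with no false calls. It is not 0.50 because progression is dated at scans and ties are handled by Breslow's method. It moves to 0.522 at the low end and 0.573 at the high end.
- In SE units: ln(0.522/0.515)/0.316 = 0.04 and ln(0.573/0.515)/0.316 = 0.34.

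These rates suppose that joint reading never stops a false call. They show what the assumptions imply and are not an estimate for this trial. If readers never call progression on a modest rise, the effect is zero.

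**The case against.** The strongest reply is that the bone bullets are signs supporting the RECIST size rule printed above them, not separate triggers. Read literally, the partial-response row would make any fall in uptake a response, which nobody intends. On this view a reader who called progression on a modest rise with stable CT would be acting against the joint-reading rule and the false-positive warning. This reading is possible and perhaps the usual one in practice, but the table does not compel it.

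Three further points have force. The tables are openly labelled as modified MDA, and the unqualified fall in the partial-response row shows that the MDA percentages were dropped in both directions. A reader might infer an undeclared departure from MDA; the documents do not support that. What is missing is an explanation of why target and non-target lesions differ. Next, the word 'substantial' may be there because non-target lesions have no measurement. That is a reasonable account, but the protocol does not give it. Last, the stable-disease row of the source MDA table has no uptake line either. There, however, the 25% threshold keeps smaller rises out of progression; once the threshold is removed, that protection goes.

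A reader might also infer that SAP section 6.7 makes matters worse, because a recorded progression is kept over a later assessment in the same window and dated at the earliest image. Those rules apply to every progression call and are not specific to uptake.

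**Conclusion.** The inconsistency is real and minor. The target-bone uptake bullet is looser than both the non-target rule and the source criteria, without explanation, and it leaves a stable lesion with a modest uptake rise fitting two categories. The consequence is at most non-differential misclassification of PFS, because central review is blinded and the same rules apply to both arms. That dilutes a true effect; it does not favour either arm. Only patients with measurable lytic or mixed bone targets are exposed, and joint reading with CT or MRI limits it further.

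The size is unknown and possibly negligible. The shift of 0.04 to 0.34 SE rests wholly on the assumed shares and false-call rates. A reader might infer that every rise in uptake was counted as progression, or that this accounts for the lack of benefit reported in Protocol section 1.4. The documents support neither inference: they contain no reading data, and an imaging charter that is not among them may settle the overlap.

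**What to change.** Insert 'substantial' in the uptake bullet of the target-bone progression row of Table 10.4: 1. Add a line to the target-bone stable-disease row for a rise or fall in uptake too small to count as progression or partial response, modelled on the existing Non-CR/Non-PD line in Table 10.4: 2. Put both in the imaging charter. Further wording on flare or CT correlation is optional, because the appendix already covers both. Central reading has ended under protocol version 6, so in practice the change serves a re-read or a successor protocol.

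The direct cost is two table rows and a charter entry, with no extra scans or readers. The downside is that a true progression visible only as a modest uptake rise may wait for a later scan. From footnote 10 of the original flow chart, bone scans fall at weeks 8, 16 and 32, then with every other CT (weeks 48, 64 and 80), then every 24 weeks. The wait is therefore 8 to 16 weeks up to week 80 and up to 24 weeks after that, unless a CT in between shows the progression. Suppose this happened to 5% to 20% of progressions among the same assumed 20% to 40% of patients, with no CT rescue. Then 0.3 to 2.5 of the 40 events would be dated late, the median HR would stay at 0.514 to 0.515, and the 40th event would come 0.1 to 0.6 months later.

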 - At least one measurable non-visceral lesion according to RECIST version 1.1 in either lymph nodes, soft tissue, skin

AND/OR

 - At least one measurable non-visceral lesion according to RECIST version 1.1 as lytic or mixed (lytic + blastic) in bone

AND/OR

- At least one non-measurable (lytic, mixed lytic + blastic, or blastic) bone lesion according to RECIST version 1.1
10. Eastern Cooperative Oncology Group (ECOG) performance score 0 or 1 ([R04-1314](#))
 11. Fasting glucose <8.9 mmol/L (<160 mg/dL) and HbA1c <8.0%
 12. Adequate organ function, defined as all of the following:
 - a) Absolute neutrophil count (ANC) $\geq 1500/\text{mm}^3$
 - b) Platelet count $\geq 100,000/\text{mm}^3$
 - c) International Normalised Ratio (INR)¹ ≤ 2.0
 - d) Serum creatinine ≤ 1.5 times upper limit of institutional normal (ULN) or creatinine clearance ≥ 50 mL/min (measured or calculated by Cockcroft and Gault formula).
 - e.) Total Bilirubin ≤ 1.5 times ULN (patients with Gilbert syndrome total bilirubin must be <4 times ULN)
 - f) Aspartate amino transferase (AST) and alanine amino transferase (ALT) ≤ 2.5 times the ULN
 - g) Fasting triglycerides ≤ 300 mg/dL or 3.42 mmol/L h) Haemoglobin (Hgb) ≥ 9.0 g/dL
 13. Recovered from any previous therapy related toxicity to \leq Grade 1 at study entry (except for stable sensory neuropathy \leq Grade 2 and alopecia)

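### Appendix 10.4 gives conflicting rules on whether a new sclerotic bone lesion is flare or progression, and the primary PFS event depends on which rule is applied

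*Protocol*

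**What the plan says.** Protocol Section 5.1 and SAP Section 5 define response and progression by RECIST 1.1 combined with MD Anderson bone criteria. The detail is in protocol Appendix 10.4. Protocol Section 7.3.1 and SAP Section 5.1 take the PD date for primary PFS from the independent read.

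On new sclerotic bone lesions, Appendix 10.4 says:

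- **Table 10.4: 5 (source criteria), partial response:** flare is "Interval visualization of lesions with sclerotic rims or new sclerotic lesions in the setting of other signs of PR and absence of progressive bony disease".
- **Table 10.4: 1 (target bone lesions), PR row:** it keeps both conditions and accepts "new sclerotic lesions in the setting of other signs of PR and absence of progressive bony disease". Its PD row asks for "The appearance of one or more new unequivocal lesions" and also lists new metastases in bone.
- **Table 10.4: 2 (non-target bone lesions), Non-CR/Non-PD row:** under the flare entry it accepts "Interval visualization of lesions with sclerotic rims or new sclerotic lesions and absence of progressive bony disease". Other signs of response are not required.
- **Table 10.4: 2, PD row:** "Appearance of one or more new lesions and/or unequivocal progression of existing non-target lesions", and for bone "New bone metastases".
- **Tables 10.4: 3 and 10.4: 4 (time-point response):** once the new-lesion column is Yes, the overall response is PD whatever the other columns say.

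The text before Table 10.4: 5 says of bone scans that "a mere lesion counting on bone scans is not sufficient and would be medical incorrect and unacceptable" and calls for bone scan and anatomical imaging to be read together.

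Inclusion criterion 9 (Section 3.3.2) allows entry on "At least one non-measurable (lytic, mixed lytic + blastic, or blastic) bone lesion according to RECIST version 1.1" alone.

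**The concern.** The same finding, a new sclerotic lesion in a patient followed for non-target bone disease, fits a row that scores it as not progressed and a row that scores it as progressed. The condition that would separate the two in the source criteria is missing from the table where it is most needed.

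At stake is whether and when a primary PFS event is scored. Read leniently, a new blastic metastasis can pass as flare. Read strictly, a healing reaction can be called PD as early as the week 8 bone scan.

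Discordant reads also have a path into censoring. Clinical decisions follow the investigator's read (Section 5.1), and radiologic PD normally ends trial treatment (Section 3.3.4.1). If the investigator calls PD, the central reader does not, and new therapy starts, SAP Table 5.1: 1 censors the patient at the last assessment before that therapy.

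Bone-only disease is a stratification factor (Section 7.6), and Section 1.3 describes the earlier trial's effect as more pronounced in that subgroup.

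**Working it through.** The point is textual, so the check is to set the rows side by side.

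| Place in Appendix 10.4 | New sclerotic lesion is flare if | New lesion is PD if |
|---|---|---|
| Table 10.4: 5 (source) | other signs of PR, and no progression in bone | stable disease excludes new bone metastases |
| Table 10.4: 1 (target) | other signs of PR, and no progression in bone | it is unequivocal, or is a new bone metastasis |
| Table 10.4: 2 (non-target) | no progression in bone | any new lesion, or a new bone metastasis |
| Table 10.4: 3 (time point, target disease) | no entry | any new lesion |
| Table 10.4: 4 (time point, non-target only) | no entry | any new lesion |

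Take a patient with only non-target bone disease, existing lesions unchanged, and one new sclerotic lesion.

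1. The Non-CR/Non-PD row of Table 10.4: 2 is met if there is no progressive disease in bone.
2. The PD row of the same table defines progression in bone partly by new metastases. To apply step 1, the reader must already have decided that the lesion is not a metastasis, which is the question. The remaining safeguard is circular.
3. Table 10.4: 4 gives Non-CR/Non-PD if the lesion is not coded as new, and PD if it is. Nothing says whether a lesion judged to be flare is coded as new.
4. Under the source wording, unchanged existing lesions show no other sign of response, so the flare row would not be met. The dropped condition is the one that bears on this case.

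**Who is exposed.** Appendix 10.4 treats bone lesions that are not lytic or mixed as non-measurable, so blastic lesions are always judged under Table 10.4: 2. The fill-in signs of healing are worded for lytic lesions, which leaves fewer response signs for blastic disease. Bone-only patients with a measurable lytic or mixed lesion are also read under Table 10.4: 1. There the conflict is milder, but it exists: flare in the PR row against new metastases in the PD row and the new-lesion row of Table 10.4: 3.

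**Whether the plan's figures size it.** Table 7.7: 1 uses P = Φ((ln t − ln HR)/√(4/D)). With D = 40 and HR = 0.50:

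- t = 0.60: 0.1823/0.3162 = 0.577, giving 71.8%.
- t = 0.75: 0.4055/0.3162 = 1.282, giving 90.0%.

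Both match the protocol. The inputs are the true HR, the threshold and the event count, so the table says nothing about how an event is defined. Sizing would need three quantities: the number of patients with only non-target bone disease, the rate of flare, and the rate of progression shown only by new sclerotic lesions, the two rates ideally by arm. The documents give none of them.

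**The case against.** The omission may be deliberate. Non-target disease has no PR category, so the source phrase could not be carried over literally. Section 5.1 says that the MD Anderson criteria are adapted, and Appendix 10.4 makes non-target assessment qualitative. The disputed line belongs to the flare entry, so it is not a general licence for new blastic lesions. The PD row speaks of metastases, a different term, and joint reading of bone scan and CT or MRI is meant to tell the two apart. Central readers were blinded, and an imaging charter may hold a rule. Section 7.7 already allows about 20% for drop-out and discordant reads together. The primary analysis is complete and central reading has stopped.

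Much of this stands as explanation. It shows why the wording differs and why bias by arm in assigning reads is limited. It does not supply a rule. The joint-reading text says what to look at, not which row prevails. The condition could have been kept as other signs of response without a PR category. A charter is not among the documents, and investigators work from Appendix 10.4. Completion of the analysis changes the form of the remedy, but the question of which rule was applied remains.

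**Conclusion.** Appendix 10.4 is internally inconsistent on new sclerotic bone lesions, and the affected event is the primary PFS event. Patients with only non-target bone disease, blastic disease included, are most exposed. This rests on the text alone and needs no numerical assumption.

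Four stronger readings are not supported.

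- **A count of lost or moved events.** A reader might multiply the bone-only share in the earlier trial (16/33 = 48%) by a guessed rate. That share includes bone-only patients who may also have target lesions, and Appendix 10.4 describes the skeletal metastases in this population as mainly osteolytic or mixed. Any rate would be invented. Section 7.3 sets the cut at about 40 independently assessed events, so unscored events would mainly delay the analysis.
- **A biased result.** Nothing in the documents shows that either reading favoured an arm.
- **Automatic PD for a new sclerotic lesion when all baseline bone lesions are blastic.** The source criteria do not say this, and it risks the false-positive progression that Appendix 10.4 warns about.
- **Certain PD for the same finding in a patient with target disease.** Table 10.4: 1 asks for an unequivocal new lesion or a new metastasis. Table 10.4: 2 covers new lesions generally, so it also reaches these patients.

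The size of the effect cannot be estimated from the documents.

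**What to change.** Reconcile the rows using the protocol's own source wording:

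- **Table 10.4: 2, Non-CR/Non-PD row:** accept new sclerotic lesions as flare only with other signs of response in existing bone lesions and no progressive disease in bone.
- **Table 10.4: 2, PD row, and Tables 10.4: 3 and 10.4: 4:** count only unequivocal new lesions that have not been classified as flare.
- **Equivocal lesions:** state how an equivocal new sclerotic lesion is carried forward, and how PD is dated if a later scheduled assessment (CT or MRI and, where due, bone scan) confirms it.
- **Blastic-only disease:** the sponsor and the imaging reviewers should state how it is handled.
- **Scope:** the same text should govern investigator and central reads.

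The cost is a few table lines and the matching reader instruction, with no new scans. The small downside is that some readings wait for a later scan and are backdated. The flow chart pairs bone scans with weeks 8, 16 and 32 but not 24 or 40. After week 16, confirmation by CT can therefore come 8 weeks later, but confirmation by bone scan may take 16.

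Because the primary analysis is complete (Section 1.4), the usable form now is to document in the trial report which reading the central readers applied and, where existing reads allow, to report PFS under both.
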